## 2. STUDY OBJECTIVES AND ENDPOINTS

Primary Objective	Primary Endpoint
Compare the efficacy of itacitinib in combination with corticosteroids versus placebo in combination with corticosteroids in terms of ORR at Day 28 in subjects with aGVHD.	ORR at Day 28, defined as the proportion of subjects demonstrating a CR, VGPR, or PR.
Key Secondary Objective	Key Secondary Endpoint
Compare the efficacy between treatment cohorts at a subsequent key clinical landmark.	NRM at Month 6, defined as the proportion of subjects who died due to causes other than malignancy relapse at Month 6.
Secondary Objectives	Secondary Endpoints
Compare additional response and longer-term efficacy outcomes between treatment cohorts.	ORR, defined as the proportion of subjects demonstrating a CR, VGPR, or PR at Days 14, 56, and 100.
	NRM at Months 9, 12, and 24.
	DOR for responders will be calculated. The DoR is defined from the time of the onset of response to loss of response. Subjects who died or discontinued will be censored at the death date or the previous assessment.
	TTR, defined as the interval from treatment initiation to first response.
	Relapse rate of malignant and nonmalignant hematologic diseases, defined as the proportion of subjects whose underlying hematologic disease relapses.
	Malignancy relapse-related mortality rate, defined as the proportion of subjects whose malignancy relapses and has a fatal outcome.
	FFS, defined as the proportion of subjects who are still alive, have not relapsed, have not required additional therapy for aGVHD, and have not demonstrated signs or symptoms of cGVHD, at Month 6.
	OS, defined as the interval from study enrollment to death due to any cause.
Assess the incidence and severity of AEs and SAEs.	Clinical safety data (eg. AEs, infections) will be tabulated and listed.
Evaluate the PK of itacitinib when administered in combination with corticosteroids.	$C_{max}$ , $C_{min}$ , $t_{max}$ , AUC, and CL/F.
Evaluate the incidence of secondary graft failure.	Incidence rate of secondary graft failure, defined as > 95% recipient cells any time after engraftment with no signs of relapse, OR retransplantation because of secondary neutropenia ( $< 0.5 \times 10^9/L$ ) and/or thrombocytopenia ( $< 20 \times 10^9/L$ ) within 2 months of transplant.

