## 9. STATISTICS

### 9.1. Study Populations

Subject enrollment, disposition, demographics, and medical history will be summarized at baseline. Dose exposure will be calculated for each dose level. Safety and disease response data will be compared over time to assess change from baseline, during treatment, and follow-up.

The populations to be analyzed include the following:

- Efficacy evaluable population: Subjects randomized into the study.
- Per-Protocol population: A subset of subjects in the efficacy evaluable population who are compliant with requirements of the clinical study Protocol, including:
  - Continued to meet all eligibility criteria on Study Day 1.
  - Initiated correct randomized therapy within the Protocol-specified window.
  - Did not significantly deviate from the Protocol in terms of missed study visits, noncompliance with randomized therapy, or prohibited concomitant medications.
- Safety evaluable population: Subjects randomized into the study who received at least 1 dose of study drug.
- Pharmacokinetic and translational research evaluable population: Subjects who receive at least 1 dose of study drug and provide at least 1 plasma sample (1 corresponding PK or translational research measurement) after study drug administration will be considered as potential PK evaluable subjects. The study pharmacokineticist will review data listings of study drug administration and sample records to identify subjects to be excluded from analyses of PK data.

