### 9.3. Level of Significance

The 1-sided significance level for the primary and key secondary endpoint analysis is 0.025. The 2-sided significance level for other analyses is 0.05. All CIs will be 95%.

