#### 9.4.2. Secondary Analyses

The key secondary endpoint is NRM at Month 6, defined as the proportion of subjects who died due to causes other than malignancy relapse at Month 6. The comparison of NRM at Month 6 between treatment cohorts will be conducted using a 2-sample proportion test with normal approximation. Summary statistics and 95% CI will be provided.

Additional secondary endpoints will be analyzed as follows:

- ORR, defined as the proportion of subjects demonstrating a CR, VGPR, or PR at Days 14, 56, and 100. The comparison between treatment cohorts will be conducted using a 2-sample proportion test with normal approximation. Summary statistics and applicable 95% CI will be provided.
- NRM, defined as the proportion of subjects who died due to causes other than malignancy relapse at Months 9, 12, and 24. The comparison between treatment cohorts will be conducted using a 2-sample proportion test with normal approximation. Cumulative incidence rates will be provided. Summary statistics and applicable 95% CI will be provided.
- DOR, defined as the time from first response until GVHD progression or death. The comparison between treatment cohorts will be conducted using the log-rank test. The Kaplan-Meier method will be used. Summary statistics will be provided.
- TTR, defined as the interval from treatment initiation to first response.
- Relapse rate of malignant and nonmalignant hematologic diseases, defined as the proportion of subjects whose underlying disease relapses. The comparison between treatment cohorts will be conducted using a 2-sample proportion test with normal approximation. The cumulative incidence rate and summary statistics will be provided.

- Relapse-related mortality rate, defined as the proportion of subjects whose malignancy relapses and has a fatal outcome. The comparison between treatment cohorts will be conducted using a 2-sample proportion test with normal approximation. The cumulative incidence rate and summary statistics will be provided.
- FFS, defined as the proportion of subjects who are still alive, have not relapsed, have not required additional therapy for aGVHD, and have not demonstrated signs or symptoms of cGVHD, at Month 6. The comparison between treatment cohorts will be conducted using the log-rank test. The Kaplan-Meier method will be used. Summary statistics will be provided.

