The first interim analysis for futility only will be performed when 112 subjects (25.7% of the planned 436 subjects) have completed the Day 28 visit or withdrew early from study. No alpha will be spent during the first interim analysis. The stopping rule is nonbinding. When the conditional power is < 20%, the sponsor may consider terminating the study if the totality of evidence is warranted. The conditional power is calculated assuming that the estimated treatment effect at the interim analysis is the true effect using the formula (Jennison and Turnbull 1999):

$$\Phi \left(\frac{z}{\sqrt{t(1-t)}} - \frac{z_{\alpha/2}}{\sqrt{1-t}} \right)$$

where Φ is the cumulative distribution function of the observed normalized test statistic z , and t is the information fraction (ie, observed sample at interim divided by the planned total sample size 436); $t = 0.257$ at Interim 1 and $z_{\alpha/2} = 1.96$.

Since CMH test with only 1 stratification factor, aGVHD risk status (standard vs high risk), will be used to test ORR at Day 28, it is thus a chi-square test with degree of freedom equal to 1, that is, $\chi^2_{df=1}$. Taking the square root of the observed CMH test statistic $\chi^2_{df=1}$ will result in normalized test statistic z .

3.4.2. Interim Analysis 2

For Interim Analysis 2, the analysis of both efficacy and futility will use a clinical database cutoff based on when 240 eligible subjects (55.0% of the targeted 436 subjects) have completed the Day 180 visit or withdrew from the study prior to Day 180.

The Hwang-Shih-DeCani alpha spending function with shape parameter -4 (O'Brian-Fleming like boundary) will be used to define upper efficacy boundary for the primary analysis of ORR at Day 28 when approximately 240 eligible subjects reach Day 180 (Hwang et al 1990). Based on enrollment projection, there will be approximately 360 subjects who have completed Day 28.

Table 2 lists efficacy boundary when information fraction (ie, the percentage of subjects) is 0.826 (360 subjects complete Day 28) at Interim 2; if ORR tested at Day 28 crosses the boundary, then the key secondary endpoint, 6-month NRM rate, will be tested by using the Bonferroni method for alpha spending (ie, 0.0125 as compared with 1-sided p-value at both interim and final analyses). By simulation, without considering early stopping for futility, the power of testing 6-month NRM at Interim 2 (with 240 eligible subjects who have completed Day 180) is approximately 0.608.

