5.3.3.1. Full Analysis Set

All subjects who are randomized constitute the FAS.

The FAS will be used for the summary of demographics, baseline characteristics, subject disposition, and analyses of all efficacy data according to intent-to-treat principle.

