7.4. Analysis of the Secondary Efficacy Endpoints

7.4.1. Key Secondary Endpoint Analysis

Nonrelapse mortality is defined as death due to causes other than malignancy relapse. For the primary analysis, the NRM rate will be estimated using the proportion of subjects with a death due to causes other than malignancy relapse within the subjects who were known alive at Day 180 or who had such a death. Reasons for not including a subject in this proportion include:

- Subject was alive and had not reached Day 180
- Death due to malignancy relapse
- Subject ended study participation prior to Day 180 (summarized by reason for study withdrawal)

A sensitivity analysis will also be conducted estimating the NRM rate using the KM estimator for each treatment.

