7.4.1.1. Primary Analysis of Nonrelapse Mortality Rate at Month 6 (Day 180)

For the primary analysis, NRM will be analyzed using a stratified CMH test. Month 6 NRM will be summarized using descriptive statistics by treatment group with 2-sided exact binomial 95% CIs. P-value, mean proportion difference, odds ratio, and 95% Wald confidence limits calculated from stratified CMH test will also be presented.

Let $\hat{p}_{pbo,i}$ be the estimated proportion of evaluable subjects in the placebo group in stratum i who died due to causes other than malignancy relapse prior to or on Day 180 (ie, excluding those subjects who are either ongoing and have not reached Day 180, who withdrew from study prior to Day 180, or who died due to relapse) with corresponding variance estimator $\hat{V}(\hat{p}_{pbo,i})$. Let $\hat{p}_{trt,i}$ and $\hat{V}(\hat{p}_{trt,i})$ be the same for the itacitinib group in stratum i .

The overall estimate of treatment difference in Day 180 NRM between placebo and itacitinib is defined as the following:

$$w * [\hat{p}_{pbo,standard} - \hat{p}_{trt,standard}] + (1 - w) * [\hat{p}_{pbo,high} - \hat{p}_{trt,high}]$$

Its 95% CI is the above estimate of difference

$$\pm 1.96 * \text{sqrt} (w^2 * (\hat{V}(\hat{p}_{pbo,standard}) + \hat{V}(\hat{p}_{trt,standard})) + (1 - w)^2 * (\hat{V}(\hat{p}_{pbo,high}) + \hat{V}(\hat{p}_{trt,high})))$$

With weight w defined by inverse of variance in 2 baseline GVHD risk groups. That is:

$$w = \frac{1/[\hat{V}(\hat{p}_{pbo,standard}) + \hat{V}(\hat{p}_{trt,standard})]}{1/[\hat{V}(\hat{p}_{pbo,standard}) + \hat{V}(\hat{p}_{trt,standard})] + 1/[\hat{V}(\hat{p}_{pbo,high}) + \hat{V}(\hat{p}_{trt,high})]}$$

7.4.1.2. Sensitivity Analysis of Nonrelapse Mortality Rate at Month 6 (Day 180) Using Kaplan-Meier Approach

A sensitivity analysis will also be conducted where NRM at Day 180 will be estimated by 1 minus the survival probability at Day 180 using the KM estimator.

A stratified test statistic for NRM rate at Day 180 is proposed as:

$$TS_{Day180NRM} = \frac{\left[\sum_{j=1}^2 (\widehat{CDF}_{pbo,j}(t=D180) - \widehat{CDF}_{trt,j}(t=D180)) \right]^2}{\sum_{j=1}^2 Var(\widehat{CDF}_{pbo,j}(t=D180) - \widehat{CDF}_{trt,j}(t=D180))}$$

$$= \frac{\left[\sum_{j=1}^2 (\widehat{CDF}_{pbo,j}(t = D180) - \widehat{CDF}_{trt,j}(t = D180)) \right]^2}{\sum_{j=1}^2 (SE(\widehat{CDF}_{pbo,j}(t = D180))^2 + SE(\widehat{CDF}_{trt,j}(t = D180))^2)}$$

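### The alpha-controlled Month 6 NRM test leaves relapse deaths out of its denominator, so it tests a different quantity from the protocol's endpoint and is distorted in either direction if relapse mortality differs between arms

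*SAP*

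**What the plan says.** Protocol Section 2 gives the key secondary endpoint as "NRM at Month 6, defined as the proportion of subjects who died due to causes other than malignancy relapse at Month 6". Protocol 9.4.2 repeats it, and SAP Table 1 carries the same definition. The protocol's efficacy population is all randomized subjects (9.1: "Efficacy evaluable population: Subjects randomized into the study"). SAP 5.3.3.1 assigns to the full analysis set (FAS) the "analyses of all efficacy data according to intent-to-treat principle".

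SAP 7.4.1 then takes the NRM proportion "within the subjects who were known alive at Day 180 or who had such a death", and its list of reasons for leaving a subject out includes death from malignancy relapse. The estimator in SAP 7.4.1.1 likewise excludes those not yet at Day 180 and those "who withdrew from study prior to Day 180, or who died due to relapse". This is the stratified CMH test that follows a positive Day 28 ORR at Interim 2 and at the final analysis (SAP 9.1.2 and 9.2), at "0.0125 as compared with 1-sided p-value at both interim and final analyses".

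SAP 10.2.1 says the Month 6 NRM definition was refined after Health Authority feedback, without describing that feedback. SAP 10.1, on changes to protocol-defined analyses, does not mention it.

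**The concern.** A subject who died of relapse by Day 180 is not missing for NRM. The outcome is known, and under the protocol definition it is a non-event. Removing that subject conditions a confirmatory test on something that happened after randomization. The reported quantity becomes NRM among those who did not die of relapse, which is a different estimand from the one in the protocol and in the SAP's own endpoint table.

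The key secondary result can then shift because relapse deaths differ by arm while crude NRM does not. Protocol 1.1 notes that treating GVHD may increase relapse, so a difference is foreseeable. The Kaplan-Meier sensitivity analysis in SAP 7.4.1.2 censors relapse deaths, so it does not test this choice.

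**Working it through.** **Inputs from the documents.** Control NRM is 22% (standard risk) and 44% (high risk), mean 33%. Itacitinib NRM is 12.4% and 28.2%, mean 20.3%; the overall planning figure is stated as 19.8%. Strata are 50:50 and allocation is 1:1, with 207 per arm evaluable and 218 per arm randomized (Protocol 9.2). The planning alpha is one-sided 0.025 (Protocol 9.3); the SAP tests NRM at one-sided 0.0125.

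**Assumed.** Relapse death by Day 180, because the documents give no rate. The values used run from 4% to 15%, the same in both strata.

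**The plan's own figure.** Two-stratum CMH power with 207 per arm at 0.025 is 82.2% with continuity correction and 85.1% without. The stated 83% is reproduced by the corrected version.

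**Effect on the rates.** With crude NRM p and relapse death r, the SAP's denominator gives p/(1 − r).
- Equal 8% relapse death: 33.0/0.92 = 35.9% and 19.8/0.92 = 21.5%. The difference is 13.2/0.92 = 14.3 points instead of 13.2.
- Equal crude NRM of 33%, relapse death 10% placebo v 5% itacitinib: 33/0.90 = 36.7% v 33/0.95 = 34.7%, an apparent benefit of 1.9 points from unrounded rates. With 5% v 10% it is an apparent harm of 1.9 points.
- Planned stratum rates, relapse death 5% v 10%: 33.0/0.95 = 34.7% v 20.3/0.90 = 22.6%, difference 12.2 points instead of 12.7. With 10% v 5%: 36.7% v 21.4%, difference 15.3.

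**Effect on the test.** Simulated stratified CMH without continuity correction, 218 per arm, one-sided 0.0125, 200,000 runs. The null is equal crude NRM (22%/44% in both arms), which is the null of the protocol's endpoint.

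| Relapse death, placebo v itacitinib | Rejection under the null | Power, planned effect |
|---|---|---|
| Relapse deaths kept in | 0.012 to 0.013 | 80% |
| 8% v 8%, excluded | 0.012 | 82% |
| 8% v 4%, excluded | 0.028 | not run |
| 10% v 5%, excluded | 0.034 | 90% |
| 12% v 6%, excluded | 0.042 | not run |
| 4% v 8%, excluded | 0.005 | not run |
| 5% v 10%, excluded | 0.004 | 71% |
| 6% v 12%, excluded | 0.003 | not run |

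**A different null.** Suppose instead that the cause-specific NRM hazards are equal and constant, with control crude NRM still 22%/44%. At 5% v 10% the full-denominator test rejects at 0.022 and the SAP's test at 0.008. At 10% v 5% the figures are 0.006 and 0.019. Relapse death is a competing event, so the full denominator responds to it as well, in the opposite direction.

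**The case against.** The strongest reply has four parts.

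1. **The change was deliberate.** SAP 10.2.1 attributes it to Health Authority feedback. That stands, and it rules out calling this an oversight or wholly undisclosed. But the feedback is not described and no reason is given for dropping relapse deaths. Table 1 still carries the protocol's definition, so the SAP contradicts itself.

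2. **Direction.** A reader might infer that the rule favours itacitinib by inflating false positives. The documents do not support that. Inflation needs fewer relapse deaths on itacitinib, while the worry in Protocol 1.1 is that GVHD treatment raises relapse. In that direction the test is conservative for equal crude NRM, and the harm is lost power.

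3. **Choice of null.** Which denominator looks distorted depends on whether the null is equal crude NRM or equal cause-specific hazards. This is correct, so restoring the full denominator restores the protocol's endpoint but does not free it from relapse mortality. It would be wrong to claim more for the fix.

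4. **Existing safeguards.** Competing-risks analyses (SAP 7.4.3) and relapse-related mortality (SAP 7.4.8) are already planned, so an imbalance would be visible. They are supportive, however, and do not decide the alpha-controlled claim.

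A reader might also infer that someone alive at Day 180 who dies of relapse later, say on Day 300, leaves the denominator, because the exclusion wording has no time limit. That reading is strained: SAP 7.4.1 includes anyone known alive at Day 180. The missing time limit is a wording gap and nothing more.

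**Conclusion.** The point holds as a mismatch of estimand on a confirmatory endpoint. The SAP's primary NRM test removes subjects whose NRM status is known. This contradicts the protocol definition and SAP Table 1, departs from the intent-to-treat rule for the FAS, and is not recorded in SAP 10.1.

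The numerical consequence is conditional. It needs a difference in relapse mortality between arms, and its sign follows that difference. At the assumed 10% v 5% and 5% v 10%, rejection is about 0.034 and 0.004 against nominal 0.0125, and power is about 90% and 71% against 80%. All of these take equal crude NRM as the null and rest on assumed relapse-death rates. With equal relapse mortality, only the reported rates and their difference rise.

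The removal of withdrawals is a separate matter: their Day 180 vital status may be unknown, so this point does not ask for them to be counted as non-events.

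**What to change.** - In SAP 7.4.1 and 7.4.1.1, count relapse deaths on or before Day 180 as NRM non-events and keep them in the denominator.
- Add the Day 180 limit to the exclusion wording, so that anyone alive at Day 180 stays in whatever happens later.
- Keep the current excluded-denominator version as a sensitivity analysis.
- Report the Day 180 cumulative incidence with relapse death as competing event (SAP 7.4.3, type II) and relapse mortality by arm beside the primary result, because the full denominator also responds to relapse death.
- Record the change in SAP 10.1 and tell the regulator, since SAP 10.2.1 attributes the current definition to its feedback.

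The cost is SAP wording, one denominator rule in the program, and slightly smaller reported NRM rates. No new data are needed.

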7.4.1.1. Primary Analysis of Nonrelapse Mortality Rate at Month 6 (Day 180)

For the primary analysis, NRM will be analyzed using a stratified CMH test. Month 6 NRM will be summarized using descriptive statistics by treatment group with 2-sided exact binomial 95% CIs. P-value, mean proportion difference, odds ratio, and 95% Wald confidence limits calculated from stratified CMH test will also be presented.

Let $\hat{p}_{pbo,i}$ be the estimated proportion of evaluable subjects in the placebo group in stratum i who died due to causes other than malignancy relapse prior to or on Day 180 (ie, excluding those subjects who are either ongoing and have not reached Day 180, who withdrew from study prior to Day 180, or who died due to relapse) with corresponding variance estimator $\hat{V}(\hat{p}_{pbo,i})$. Let $\hat{p}_{trt,i}$ and $\hat{V}(\hat{p}_{trt,i})$ be the same for the itacitinib group in stratum i .

The overall estimate of treatment difference in Day 180 NRM between placebo and itacitinib is defined as the following:

$$w * [\hat{p}_{pbo,standard} - \hat{p}_{trt,standard}] + (1 - w) * [\hat{p}_{pbo,high} - \hat{p}_{trt,high}]$$

Its 95% CI is the above estimate of difference

$$\pm 1.96 * \text{sqrt} (w^2 * (\hat{V}(\hat{p}_{pbo,standard}) + \hat{V}(\hat{p}_{trt,standard})) + (1 - w)^2 * (\hat{V}(\hat{p}_{pbo,high}) + \hat{V}(\hat{p}_{trt,high})))$$

With weight w defined by inverse of variance in 2 baseline GVHD risk groups. That is:

$$w = \frac{1/[\hat{V}(\hat{p}_{pbo,standard}) + \hat{V}(\hat{p}_{trt,standard})]}{1/[\hat{V}(\hat{p}_{pbo,standard}) + \hat{V}(\hat{p}_{trt,standard})] + 1/[\hat{V}(\hat{p}_{pbo,high}) + \hat{V}(\hat{p}_{trt,high})]}$$

7.4.1.2. Sensitivity Analysis of Nonrelapse Mortality Rate at Month 6 (Day 180) Using Kaplan-Meier Approach

A sensitivity analysis will also be conducted where NRM at Day 180 will be estimated by 1 minus the survival probability at Day 180 using the KM estimator.

A stratified test statistic for NRM rate at Day 180 is proposed as:

$$TS_{Day180NRM} = \frac{\left[\sum_{j=1}^2 (\widehat{CDF}_{pbo,j}(t=D180) - \widehat{CDF}_{trt,j}(t=D180)) \right]^2}{\sum_{j=1}^2 Var(\widehat{CDF}_{pbo,j}(t=D180) - \widehat{CDF}_{trt,j}(t=D180))}$$

$$= \frac{\left[\sum_{j=1}^2 (\widehat{CDF}_{pbo,j}(t = D180) - \widehat{CDF}_{trt,j}(t = D180)) \right]^2}{\sum_{j=1}^2 (SE(\widehat{CDF}_{pbo,j}(t = D180))^2 + SE(\widehat{CDF}_{trt,j}(t = D180))^2)}$$

$\widehat{CDF}_{pbo,j}(t = D180)$ and $SE(\widehat{CDF}_{pbo,j}(t = D180))^2$ are the cumulative distribution function estimate at Day 180 in the placebo group in the jth stratum and its variance, respectively.

$\widehat{CDF}_{trt,j}(t = D180)$ and $SE(\widehat{CDF}_{trt,j}(t = D180))^2$ are defined similarly in the itacitinib group for jth stratum subjects. $TS_{Day180NRM}$ will be asymptotically distributed as a Chi-square test statistic with degree of freedom equal to 1.

The overall estimate of treatment difference in Day 180 NRM between placebo and itacitinib is thus defined as the following:

$$w * [\widehat{CDF}_{pbo,standard}(t = D180) - \widehat{CDF}_{trt,standard}(t = D180)] + (1 - w) * [\widehat{CDF}_{pbo,high}(t = D180) - \widehat{CDF}_{trt,high}(t = D180)]$$

Its 95% CI is the above estimate of difference

$$\pm 1.96 * \sqrt{w^2 * (SE(\widehat{CDF}_{pbo,standard}(t = D180)))^2 + (SE(\widehat{CDF}_{trt,standard}(t = D180)))^2 + (1 - w)^2 * (SE(\widehat{CDF}_{pbo,high}(t = D180)))^2 + SE(\widehat{CDF}_{trt,high}(t = D180))^2)}$$

with weight w defined by inverse of variance in two baseline GVHD risk groups. That is:

$$w = \frac{1/[SE(\widehat{CDF}_{pbo,standard}(t=D180))^2 + SE(\widehat{CDF}_{trt,standard}(t=D180))^2]}{1/[SE(\widehat{CDF}_{pbo,standard}(t=D180))^2 + SE(\widehat{CDF}_{trt,standard}(t=D180))^2] + 1/[SE(\widehat{CDF}_{pbo,high}(t=D180))^2 + SE(\widehat{CDF}_{trt,high}(t=D180))^2]}$$

In order to conduct above hypothesis testing for NRM at Day 180, time to NRM, defined as the interval between randomization and death due to causes other than malignancy relapse, will be derived. All subjects in the FAS without a death due to causes other than malignancy relapse will be censored at either study withdrawal, death due to malignancy relapse, or the date of last contact before or on the cutoff date, whichever is earliest.

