Given its clinical significance, NRM rate at Month 6 will be assessed as the key secondary endpoint. The Day 180 NRM rate difference between 2 groups is tested using a KM estimator of the cumulative distribution function at Day 180. Based on MacMillan et al (2015), the overall NRM at Month 6 in the best available therapy group is 33%, with a stratum-specific NRM rate of 22% for standard risk and 44% for high risk (assuming a standard risk:high risk ratio of 0.50:0.50). A 40% relative reduction in NRM rate will be considered a clinically meaningful improvement. Based on simulation, a sample size of 414 subjects (207 subjects per treatment cohort) will provide approximately 80% power to detect a relative reduction of 40% (or absolute difference of 13.2%, ie, 19.8% vs 33% at Day 180) between treatments at a 1-sided α level of 0.025. NRM at Month 6 will be tested using a CMH test stratified by risk status (standard-risk vs high-risk aGVHD). Stratum-specific NRM rates of 12.4% and 28.2% are expected for standard-risk and high-risk cohorts, respectively. Power for the CMH test with stratification based on GVHD risk score was calculated using software N-Query 5.0.

In order to compensate for an anticipated early withdrawal rate of up to 5% (ie, subjects who do not have any response data before Day 28), a total of 436 subjects (218 per treatment arm) will be randomized into the study to ensure a sample size of 414 evaluable subjects.

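### SAP 7.4.1.2: the Kaplan-Meier test of Day 180 NRM weights the two risk strata equally but its estimate and 95% CI use inverse-variance weights, so test and interval can disagree

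*SAP*

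**What the plan says.** SAP 7.4.1.1 sets the primary test: "For the primary analysis, NRM will be analyzed using a stratified CMH test". Its accompanying overall difference and 95% CI combine the strata by inverse variance.

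SAP 7.4.1.2 then adds the Kaplan-Meier version: "A sensitivity analysis will also be conducted where NRM at Day 180 will be estimated by 1 minus the survival probability". The test is introduced with "A stratified test statistic for NRM rate at Day 180 is proposed as". Writing d for the placebo-minus-itacitinib difference in a stratum and V for its variance, the formula is (d_standard + d_high)² / (V_standard + V_high). No weight appears. The statistic "will be asymptotically distributed as a Chi-square test statistic with degree of freedom equal to 1".

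The same section presents the overall difference as following from this, but builds it and its CI "with weight w defined by inverse of variance in two baseline GVHD risk groups".

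The planning rates are in SAP 3.3: for placebo, a "stratum-specific NRM rate of 22% for standard risk and 44% for high risk (assuming a standard risk:high risk ratio of 0.50:0.50"). For itacitinib, "Stratum-specific NRM rates of 12.4% and 28.2% are expected for standard-risk and high-risk cohorts, respectively".

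**The concern.** A plain sum gives each stratum the same weight whatever its size. The interval gives more weight to the stratum estimated more precisely. The p-value and the CI reported side by side therefore describe two different averages of the stratum effects, and one can be significant when the other is not.

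The analysis is there to show whether the CMH result survives when subjects left out of the CMH denominator are censored instead. If the stratum weighting changes at the same time, a discordant result cannot be put down to censoring. Under marked imbalance the small stratum also supplies most of the test's variance, so the analysis could look negative because of its weighting.

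**Working it through.** **Inputs.** SAP 3.3: placebo 22% / 44%, itacitinib 12.4% / 28.2%, 50:50 strata, 207 evaluable or 218 randomized per arm, "between treatments at a 1-sided α level of 0.025". Assumptions: binomial variances, complete follow-up unless stated, and splits other than 50:50.

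- d_s = 0.22 − 0.124 = 0.096; d_h = 0.44 − 0.282 = 0.158; sum 0.254.
- With n per arm and standard-risk share f: V_s = (0.22×0.78 + 0.124×0.876)/(nf) = 0.2802/(nf); V_h = (0.44×0.56 + 0.282×0.718)/(n(1−f)) = 0.4489/(n(1−f)).
- Power = Φ(z − 1.96), with z = Σw_j d_j / √(Σw_j² V_j).

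**The plan's own figures.** SAP 3.3 gives about 80% at N=414 and protocol 9.2 gives 0.811 at N=436 for the Kaplan-Meier test, both by simulation.
- N=414: z = 0.254/√(0.002707 + 0.004337) = 3.026, power 85.7%.
- N=436: z = 0.254/√(0.002571 + 0.004118) = 3.106, power 87.4%.

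Neither reproduces with complete follow-up. Simulated Kaplan-Meier data with 25% censoring by Day 180 (an assumed rate) give 80.2% and 82.4%. The stated figures are plausible but depend on a censoring rate that is not given.

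**Weights at the planned split (N=436).** Inverse variance puts w = 0.004118/(0.002571 + 0.004118) = 0.616 on standard risk. The CI centres on 0.616×0.096 + 0.384×0.158 = 0.120, SE 0.0398. The test implies w = 0.5, a difference of 0.254/2 = 0.127 and SE √0.006689/2 = 0.0409.

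**Example of disagreement.** 240 subjects, 80:20, so 96 and 24 per arm; observed rates equal to planned.
- Test: V_s = 0.002919, V_h = 0.018703; z = 0.254/√0.021622 = 1.727, chi-square 2.98, 2-sided p = 0.084. High risk is 20% of subjects and 0.018703/0.021622 = 86.5% of the variance.
- Interval: w = 0.865, estimate 0.104, SE 0.0502, CI 0.006 to 0.203.

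In simulation at N=436 with 0 to 25% censoring, the 1-sided 0.025 test and the CI disagreed in about 4–6% of trials at 50:50, 14–17% at 70:30 and 25–26% at 80:20.

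**Power, 218 per arm, 1-sided 0.025, complete follow-up.** Worked row, 80:20: V_s = 0.001607, V_h = 0.010295. Equal weights: z = 0.254/√0.011902 = 2.328, power 64.4%. Size weights: z = (0.8×0.096 + 0.2×0.158)/√(0.64×0.001607 + 0.04×0.010295) = 0.1084/0.03795 = 2.856, power 81.5%.

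| Standard:high | Equal (SAP test) | Stratum size | Inverse variance (SAP CI) |
|---|---|---|---|
| 30:70 | 84.8% | 90.3% | 88.9% |
| 40:60 | 87.6% | 89.0% | 87.1% |
| 50:50 | 87.4% | 87.4% | 85.4% |
| 60:40 | 84.5% | 85.7% | 83.6% |
| 70:30 | 77.7% | 83.7% | 81.8% |
| 80:20 | 64.4% | 81.5% | 79.9% |

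**Type I error.** Simulated rejection under the null at N=436 with 10% censoring was about 2.4% at 50:50 and 2.8% at 80:20, similar for equal and inverse-variance weights.

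**The case against.** The strongest reply is that nothing decisive depends on this statistic. SAP 7.4.1.1 makes the stratified CMH test primary, and SAP 9.1.2 carries the Section 7.4.1 method into Interim 2. Equal stratum weighting is a valid standardisation, and type I error stays near nominal. Stratified log-rank and Cox analyses of NRM (7.4.2) and competing-risks analyses (7.4.3) sit beside it, so an odd Kaplan-Meier p-value would not stand alone. All of this holds, and it limits the point to coherence and efficiency.

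Several stronger readings are tempting but not supported:

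- *The confirmatory NRM test is affected.* SAP 3.3 still says the difference is tested with a Kaplan-Meier estimator, but the same paragraph and 7.4.1.1 name the CMH test. That wording needs reconciling, but it does not make the Kaplan-Meier statistic confirmatory.
- *Power falls whenever the strata are unequal.* At 40:60 the SAP test has 87.6%, no lower than at 50:50. Against the SAP's own inverse-variance weights it is about 2 points better at 50:50 and 1 point better at 60:40.
- *The whole fall in power is due to weighting.* Size-weighted power also falls, from 87.4% to 81.5% at 80:20, because the case mix changes. Only the gap within a row is due to weighting.
- *The Bonferroni level of 0.0125 applies here.* SAP 3.4.2 and 9.1.2 assign it to the confirmatory NRM test; no document assigns it to this sensitivity analysis.
- *The strata were in fact unbalanced.* The documents do not say.

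**Conclusion.** The mismatch is real and visible in the formulas: even at the planned 50:50 split the test targets 0.127 and the interval 0.120. Its consequence there is small. The two conclusions differ in about 1 trial in 20, and no power is lost against stratum-size weights. It becomes material only under marked imbalance: about 6 points at 70:30 (77.7% vs 83.7%) and 17 at 80:20 (64.4% vs 81.5%), with conflict between test and interval in about a quarter of trials at 80:20. These sizes rest on the planned stratum rates and assumed splits, and the power figures also on complete follow-up. The point is minor. It concerns the coherence and efficiency of a sensitivity analysis, not the validity of the NRM claim.

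**What to change.** In 7.4.1.2 use one set of weights throughout: Z = Σw_j d_j / √(Σw_j² V_j), with the estimate Σw_j d_j / Σw_j and its CI from the same w_j. Fix the choice before unblinding.

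Stratum-size (Mantel-Haenszel) weights are preferable because they match the CMH primary test and lose no power at 50:50. Apply the same weights to the overall difference and CI in 7.4.1.1, which now pairs a CMH test with inverse-variance weights. If only 7.4.1.2 were changed, the primary and sensitivity estimates would differ partly through weighting. Keeping inverse-variance weights and aligning the 7.4.1.2 test to them would also be coherent within that section, at about 2 points less power at 50:50.

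The cost is a formula edit in each section and one line of code for the test. The downside of stratum-size weights is a slightly wider CI: SE about 0.041 instead of 0.040 at 50:50.
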